13.1.4 Unexpected Adverse Reactions

An adverse reaction is ‘unexpected’ if its nature and severity are not consistent with the information about the medicinal product in question as described in the most recent IB or the product information for ertapenem, levofloxacin (or the alternative PO antibiotic, if applicable).

13.2 AE Collecting and Reporting

All AEs spontaneously reported by the subject and/or in response to an open question from study personnel or revealed by observation, physical examination or other diagnostic procedures will be recorded on the appropriate page of the eCRF starting from the time of initial informed consent. Any clinically relevant deterioration in laboratory assessments or other clinical findings is considered an AE and must be recorded on the appropriate pages of the eCRF starting from the time of initial informed consent. When possible, signs and symptoms indicating a common underlying pathology should be noted as one comprehensive event.

All SAEs that occur during the course of the study, as defined by the protocol, must be reported by the Investigator to the Sponsor or its pharmacovigilance designee/contract research organization (CRO) within 24-h from the point in time when the Investigator becomes aware of

the SAE. In addition all SAEs, including all deaths, which occur from the time of signing of the informed consent up to and including 30 days after administration of the last dose of study drug, must be reported to the Sponsor or its designated CRO within 24-h. All SAEs and deaths must be reported whether or not considered causally related to the study drug. The information collected will include a minimum of the following: subject number, a narrative description of the event, and an assessment by the Investigator as to the severity of the event and relatedness to study drug. Follow-up information on the SAE may be requested by the Sponsor or its representative CRO. Detailed instructions for the collecting and reporting of SAEs will be provided in the Investigator Site File.

If there are serious, unexpected ADRs associated with the use of the study drug, appropriate regulatory agencies, all participating Investigators, as well as central IRBs/IECs will be notified on an expedited basis (7 days for fatal or life-threatening serious, unexpected ADRs). Local IRBs/IECs will be notified of all unexpected, serious ADRs involving risk to human subjects in accordance with the rules and regulations of the local IRB/IEC. Details of reporting responsibilities will be outlined in the study-specific Safety Management Plan.

An unexpected event is one that is not reported in the IB or the relevant prescribing information.

Reporting of SAEs and Suspected Unexpected Serious Adverse Reactions (SUSARs)

All SAEs must be reported to the designated CRO within 24-h of the investigational site's knowledge of the occurrence. Each investigational site will submit the SAE information to the CRO on the applicable form.

The SAE information transmitted to the CRO will include the following (as available):

- Subject number, Investigator name, and site number
- SAE information: event term, onset date, severity, and casual relationship
- Basic demographic information (e.g., age, gender, weight, etc.)
- The outcomes attributable to the event [e.g., death, a life-threatening adverse drug experience, in-patient hospitalization or prolongation of existing hospitalization, a persistent or significant disability/incapacity, other important medical event(s)]
- A summary of relevant test results, pertinent laboratory data, and any other relevant medical history
- The first and last dates of study drug administration
- A statement whether study drug was discontinued or study drug administration schedule was modified
- A statement whether event recurred after reintroduction of study drug if administration had been discontinued or withheld

- Supplemental information may include the following hospital records: laboratory results, radiology reports, progress notes, admission and emergency room notes, holding/observation notes, discharge summaries, autopsy reports, and death certificates

The SAE information should be transmitted within 24-h with as much of the above information as available at the time. Supplemental information may be transmitted and should not delay the initial transmission. The Sponsor or CRO may contact the investigational site to solicit additional information or follow-up on the event. Investigational sites will be provided with detailed instructions on the procedures for transmitting SAEs to the CRO.

For regulatory purposes, initial reports of serious ADRs should be transmitted within the prescribed time frame as long as the following minimum information is available: subject identification, suspect study drug, reporting source, and an event or outcome that can be identified as being both serious and unexpected for which, in the Investigator's opinion, there is a suspected causal relationship.

A suspected unexpected serious adverse reaction (SUSAR) which is fatal or life-threatening must be reported to the competent authority and ethics committee immediately (within 7 days) after the Sponsor becomes aware of the event. Any additional information must be reported within eight days of sending the first report.

A SUSAR which is not fatal or life-threatening must be reported to the competent authority and ethics committee as soon as possible (within 15 days) after the Sponsor becomes aware of the event.

All SUSARs occurring at the site will be entered into the European database established in accordance with Article 11 of the European Union Clinical Trials Directive (14).

13.3 Grading of Adverse Events

The severity of each AE will be categorized using the following criteria:

Mild	AE usually transient and requires no special treatment and does not interfere with the subject's daily activities.
Moderate	AE produces a low level of inconvenience to the subject and may interfere with daily activities. These events are usually ameliorated by simple therapeutic measures.
Severe	AE interrupts daily activity and requires systemic drug therapy or other medical treatment.

Key: AE = adverse event

13.4 Relationship to Study Drug

For each reported AE, the Investigator must make an assessment of the relationship of the event to the study drug using the following scale:

Not Related: An event that is definitely not associated with study drug administration and is judged clearly due to causes other than the study drug.

Unlikely Related: An event that follows a temporal sequence from administration of the study drug, such that, a relationship is not likely and could be reasonably explained by the subject's clinical state, or other modes of therapy administered to the subject.

Possibly Related: An event that follows a reasonable temporal sequence from administration of the study drug, but that may be due to another cause and could also be reasonably explained by the subject's clinical state, or other modes of therapy administered to the subject.

Probably Related: An event that follows a reasonable temporal sequence from administration of the study drug, that is not easily explained by another cause (such as, known characteristics of the subject's clinical state or other treatment) and is confirmed by improvement on stopping or slowing administration of the study agent (i.e., de-challenge, if applicable).

Definitely Related: An event that is clearly associated with study drug administration.

In the event of death, the cause of death should be recorded as the AE. "Death" is an outcome and is NOT the AE. The only exception is "sudden death" when the cause is unknown.

13.5 Laboratory Test Abnormalities

All central laboratory data generated by the study will be included in standard Statistical Analysis System (SAS) datasets. Throughout this study, subjects will have samples sent to local laboratories and to the central laboratory. Only the values from the samples sent to the central laboratory will be captured in the laboratory values database and used for the safety analysis. Investigators may report AEs based upon local laboratory values. In this event, the actual value and the normal range for the local laboratory should be recorded on the AE form.

13.6 Follow-up of Adverse Events

All AEs (regardless of relationship to study drug) and SAEs determined not to be study drug related (i.e., not related and unlikely related) will be followed through the FU visit and be noted as "Not Recovered/Not Resolved" if not resolved at this visit. Any SAE that is determined to be study drug related (possibly, probably, or definitely related) will be followed until resolution or stabilization.

The outcome of AEs will be rated as:

- Recovered/Resolved
- Recovering/Resolving
- Not Recovered/Not Resolved
- Recovered/Resolved with Sequelae
- Fatal
- Unknown

And subjects will be referred to their primary care doctor as needed post-study.

14. EVALUATION OF EFFICACY

14.1 Analysis Populations

The following definitions will be used in assigning subjects into study populations:

- ITT population – all randomized subjects
- Micro-ITT population – All subjects in the ITT population who have at least one baseline bacterial pathogen on culture of urine or blood that causes cUTI against which the investigational drug and control drug have expected antibacterial activity. Subjects should not be excluded from this population based upon events that occurred post-randomization (e.g., loss to follow-up)
- Micro-MITT population – All subjects in the micro-ITT population who receive at least one dose of study drug
- CE populations – All subjects in the ITT population who meet key inclusion/exclusion criteria, receive correct study drug, have a clinical outcome assessed, and follow other important components of the trial. Specific details are included in the statistical analysis plan (SAP)
- ME populations – All subjects in the micro-ITT population who meet key inclusion/exclusion criteria, receive correct study drug, have a microbiologic outcome assessed, and follow other important components of the trial. Specific details are included in the SAP
- Safety population – all randomized subjects who receive any amount of study drug

14.2 Efficacy Evaluations

The following primary efficacy evaluations will be performed:

- Responder outcome (clinical cure and microbiological success) at the EOI and TOC visits in the following populations:
 - Micro-ITT
- For EMA: microbiological response at the TOC visit in the following populations:
 - Micro-MITT
 - ME

The following secondary evaluations will be performed:

- Responder outcome at Day 5 in the micro-ITT population
- Clinical outcome at Day 5, EOI, EOT, TOC, and FU visits in the following populations:
 - ITT
 - CE
 - Micro-ITT
 - Micro-MITT
 - ME

- Microbiologic outcome at Day 5, EOI, EOT, TOC, and FU visits in the following populations:
 - Micro-ITT
 - Micro-MITT
 - ME
- To assess safety and tolerability of eravacycline administration in the safety population
- PK parameters after eravacycline infusion, including
 - C_{max} , time to C_{max} (T_{max}), C_{trough} , and area under the plasma concentration-time curve (AUC)

14.2.1 Clinical Outcome

Clinical outcome will be assessed at the Day 5, EOI, EOT, TOC, and FU visits. Clinical outcomes will be classified as cure, failure, indeterminate, or missing (Section 11.1.5). A favorable clinical response is “cure”.

14.2.2 Per Pathogen Microbiological Outcomes

Per pathogen microbiological outcome will be determined for the Day 5, EOI, EOT, TOC, and FU visits. Outcomes will be classified as success, failure, or indeterminate/missing based on the microbiologic response definitions (Section 11.1.7).

All purified bacterial pathogens cultured from clinical specimens will be evaluated for susceptibility to study drugs and the emergence of resistance and overgrowth of non-susceptible organisms.

14.2.3 Per Subject Microbiological Outcomes

Per subject microbiological outcomes will be determined by the per pathogen microbiological outcomes.

An overall microbiological outcome will be assessed as success, failure, or indeterminate/missing for each subject. For subjects from whom only one pathogen is isolated, the overall microbiological outcome will be based on the assessment for that pathogen. For subjects from whom more than one pathogen is isolated, the overall microbiological outcome will reflect the worst outcome present amongst all baseline pathogens.

15. STATISTICAL METHODS

A detailed SAP will be used to guide the analysis and reporting of data collected in this study.

15.1 Data Collection and Processing

An IXRS system will be used to allocate treatment assignments to subjects. Creation and validation of the clinical database, data entry, data management, and transfer of central

laboratory data will be conducted in accordance with 21 Code of Federal Regulations (CFR) Part 11 and the Guidance for Industry on Computerized Systems Used in Clinical Trials. eCRFs will be completed for all randomized subjects. Demography and end of study pages will be completed for subjects who are randomized but not treated.

15.2 Statistical Methodology

All data collected in this study will be presented in data listings and, where indicated, tabulated in summary tables. Data will be presented and summarized using the SAS System (SAS Institute Inc, Cary, NC).

Continuous variables will be summarized with the number of observations, mean, standard deviation, median, minimum, and maximum.

Categorical variables will be summarized with frequencies and percentages. Percentages will be based on non-missing data unless specified otherwise.

Except where indicated in the SAP, Baseline is defined as the most recent value prior to the start of treatment with study drug.

15.2.1 Efficacy Analyses

The co-primary efficacy outcome measures are responder outcome in the micro-ITT population at the EOI and TOC visits (defined as 14-17 days after randomization). The responder rate will be determined as the number of subjects with clinical cure (i.e., complete or significant improvement of signs or symptoms such that no rescue/non-study antibacterial treatment is required) and microbiological success at the respective visit divided by the number of subjects in the analysis population (i.e., overall or by randomization strata). The number and percentage of subjects in each treatment group classified as a responder, non-responder and indeterminate at the EOI and TOC visits will be tabulated by treatment group in the micro-ITT population. Two-sided 95% CIs for the observed difference in responder rates (eravacycline treatment group minus ertapenem treatment group) at the EOI and TOC visits will be calculated using the method without stratification of Miettinen and Nurminen. If the lower limit of both 95% CIs for the difference in responder outcomes in the micro-ITT population exceeds -10%, then non-inferiority of eravacycline to ertapenem will be declared. The primary efficacy outcome will also be assessed across the randomization stratification factors of: (1) primary site of infection (pyelonephritis and normal urinary tract anatomy vs all other diagnoses) and (2) receipt of a single dose of effective non-study antibiotics for the acute cUTI within 72 hours prior to randomization. For each site of infection and prior antibiotic stratum, a 2-sided 95% CI for the observed difference in responder rates at the EOI and TOC visits will be calculated for the micro-ITT population.

For the EMA, the co-primary efficacy outcome measures are microbiological success in the micro-MITT and ME populations at the TOC visit. The microbiological success rate will be determined as the number of subjects with microbiological success at the TOC visit divided by the number of subjects in the analysis population. The number and percentage of subjects in each treatment group classified as a microbiological success, failure and indeterminate at the TOC visit will be tabulated by treatment group in the micro-ITT and ME populations. Two-sided 99% CIs for the observed difference in success rates (eravacycline treatment group minus ertapenem treatment group) at the TOC visit in the micro-MITT and ME populations will be calculated using the method with stratification of Miettinen and Nurminen. If the lower limit of both 95% CIs for the difference in success rates exceed -10%, then non-inferiority of eravacycline to ertapenem will be declared.

The number and percentage of subjects in each treatment group with a secondary efficacy outcome of clinical cure, failure and indeterminate will be presented for Day 5, EOI, EOT, TOC and FU for the ITT, CE, micro-ITT, micro-MITT and ME populations. Two-sided 95% unstratified CIs will be constructed for the observed difference in the clinical cure rates between the treatment groups for descriptive purposes; no conclusion of NI will be made. Analyses at the TOC Visit will also be presented by the stratification factors of primary site of infection and receipt of a single dose of effective non-study antibiotics for the acute cUTI within 72 h prior to randomization.

Per-subject microbiological response will be summarized as success, failure and indeterminate at Day 5, EOI, EOT the EOT and TOC Visits in the micro-ITT, micro-MITT and ME Populations. Two-sided 95% unstratified CIs will be constructed for the observed difference in the rates of microbiological success between the treatment groups for descriptive purposes; no conclusion of NI will be made.

Time to resolution of signs and symptoms will be analyzed using Kaplan-Meier methods in the micro-ITT population. The median, 25th and 75th percentile will be presented by treatment group as will the Kaplan-Meier curve.

Microbiologic outcome by baseline pathogen will be determined as the proportion of subjects with a microbiologic success at EOI and the TOC visits for each pathogen isolated at baseline in the micro-ITT, micro-MITT and ME populations.

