Efficacy Assessments

Responder rates will be determined for each treatment arm overall and for the randomization stratification factors: (1) primary site of infection (pyelonephritis and normal urinary tract anatomy vs. all other diagnoses) and (2) receipt of a single dose of effective non-study antibiotics for the acute cUTI within 72 hours prior to randomization. The responder rate will be determined as the number of subjects with clinical cure (i.e., complete or significant improvement of signs or symptoms such that no further systemic antibiotic treatment is required) and microbiological success at the respective visit divided by the number of subjects in the analysis population (i.e., overall or by randomization strata). A two-sided 95% CI around the difference in the eravacycline and ertapenem responder rates will be determined using the Miettinen and Nurminen method. If the lower bound of the 95% CI for the difference in responder rates at EOI and TOC in the micro-ITT population is above -10% for both time points, noninferiority of eravacycline to ertapenem will be concluded.

For the EMA, the microbiological success rate will be determined as the number of subjects with microbiological success at the respective visit divided by the number of subjects in the analysis population. Microbiological success rates at TOC will be determined, along with two-sided 99% CIs, by treatment arm for subjects in the micro-MITT and ME populations. If the lower bound of the 99% CI for the difference in microbiological success rates at TOC is above -10% for both the micro-MITT and ME populations, noninferiority of eravacycline to ertapenem will be concluded.

Clinical outcome and microbiological outcome will be summarized by treatment group, time point and analysis population. Two-sided 95% CIs for the difference between treatment groups in clinical cure and microbiological success will be provided.

Microbiology

Purified bacterial pathogens aerobically cultured from urine using a calibrated loop to identify a quantitative count of bacteria at a lower limit of 10^3 CFU/mL and aerobic and anaerobic blood culture pathogens will be evaluated for susceptibility and the emergence of resistance to study drugs and overgrowth of non-susceptible organisms at a central laboratory.

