15.3 Sample Size Considerations

This study is designed to demonstrate non-inferiority of eravacycline to ertapenem in the co-primary efficacy measures of responder outcome at the EOI and TOC visits in the micro-ITT population. An NI margin of 10% will be used which is based on historical data regarding the treatment effect of antibiotics. A 10% NI margin for the efficacy measure of responder outcome is robust and can sufficiently confirm a clinically meaningful treatment effect of eravacycline in the treatment of cUTI.

The sample size calculation is based on ensuring sufficient power for the co-primary efficacy outcomes for the FDA as well as the co-primary efficacy outcomes for the EMA (which are secondary efficacy outcomes for the FDA). Using a 10% non-inferiority margin, one-sided alpha of 0.025, 80% power, response rates at TOC of 71% in the eravacycline group and 72% in the ertapenem group, and the sample size methodology of Farrington and Manning, a total of 395 subjects per arm in the micro-ITT population is required. This sample size provides >90% power for the response rates at EOI assuming the response rates are 93% and 94% in the eravacycline and ertapenem groups, respectively. A sample size of approximately 1200 randomized subjects should

provide sufficient numbers for this study, assuming 66% of enrolled subjects will meet the requirements for inclusion in the micro-ITT population.

For the EMA, it is assumed that 65% of the randomized subjects will be in the micro-MITT population and 60% in ME population. The microbiological success rates at TOC are assumed to be 79% and 82% in both treatment groups in the micro-MITT and ME populations, respectively. With these assumptions, using a non-inferiority margin of 10%, a one-sided alpha of 0.005, and the sample size methodology of Farrington and Manning, there is at least 80% power to show non-inferiority for the co-primary efficacy outcomes. The power calculations are summarized in Table 4 below based on a total of 1200 randomized subjects:

Table 4: Assumptions for Sample Size Calculations

Outcome/Population	Alpha level (one-sided)	Evaluability Rate	Outcome Rates		Total N	Power
			ERV	ERT		
FDA Outcomes						
Responder at EOI/micro-ITT	0.025	66%	93%	94%	790	>99%
Responder at TOC/micro-ITT	0.025	66%	71%	72%	790	80.0%
EMA Outcomes						
Clinical Cure at TOC/micro-MITT	0.005	65%	79%	79%	780	79.8%
Clinical Cure at TOC/ME	0.005	60%	82%	82%	720	84.7%

ERV=Eravacycline; ERT=Ertapenem

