4. GENERAL STATISTICAL METHODS

4.1. Sample Size Justification

This study is designed to demonstrate NI of eravacycline to ertapenem in the co-primary efficacy measures of responder outcome at the EOI and TOC visits in the micro-ITT population. An NI margin of 10% will be used which is based on historical data regarding the treatment effect of antibiotics. A 10% NI margin for the efficacy measure of responder outcome is robust and can sufficiently confirm a clinically meaningful treatment effect of eravacycline in the treatment of cUTI.

The sample size calculation is based on ensuring sufficient power for the co-primary efficacy outcomes for the FDA as well as the co-primary efficacy outcomes for the EMA (which are secondary efficacy outcomes for the FDA). Using a 10% NI margin, one-sided alpha of 0.025, 80% power, response rates at TOC of 71% in the eravacycline group and 72% in the ertapenem group, and the sample size methodology of Farrington and Manning, a total of 395 subjects per arm in the micro-ITT population is required. This sample size provides >90% power for the response rates at EOI assuming the response rates are 93% and 94% in the eravacycline and ertapenem groups, respectively. A sample size of approximately 1200 randomized subjects should provide sufficient numbers for this study, assuming 66% of enrolled subjects will meet the requirements for inclusion in the micro-ITT population.

For the EMA, it is assumed that 65% of the randomized subjects will be in the micro-MITT population and 60% in ME population. The microbiological success rates at TOC are assumed to be 79% and 82% in both treatment groups in the micro-MITT and ME populations, respectively. With these assumptions, using an NI margin of 10%, a one-sided alpha of 0.005, and the sample size methodology of Farrington and Manning, there is at least 80% power to show NI for the co-primary efficacy outcomes. The power calculations are summarized in [Table 3](#) based on a total of 1200 randomized subjects.

Table 3 Assumptions of Sample Size Calculations

Outcome/Population	Alpha level (one-sided)	Evaluability Rate	Outcome Rates		Total N	Power
			ERV	ERT		
FDA Outcomes						
Responder at EOI/micro-ITT	0.025	66%	93%	94%	790	>99%
Responder at TOC/micro-ITT	0.025	66%	71%	72%	790	80.0%
EMA Outcomes						
Microbiological Success at	0.005	65%	79%	79%	780	79.8%

TOC / micro-MITT						
Microbiological Success at TOC / ME-TOC	0.005	60%	82%	82%	720	84.7%

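### The EMA non-inferiority decision in Protocol 15.2.1 is read from 95% intervals, although the analysis is planned and powered on 99% intervals, so each comparison is tested at five times the planned one-sided alpha

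*Protocol*

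**What the plan says.** Protocol 15.2.1 (Efficacy Analyses) gives the EMA analysis its own paragraph. The outcome is microbiological success at TOC in the micro-MITT and ME populations, and both populations must meet the margin. The planned intervals are: "Two-sided 99% CIs for the observed difference in success rates". The sentence that follows states the decision rule with a different level: "If the lower limit of both 95% CIs for the difference in success rates exceed -10" percent, non-inferiority is declared.

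The other statements of the EMA level are:

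- **Protocol synopsis (section 2, Efficacy Assessments):** "If the lower bound of the 99% CI for the difference in microbiological success rates at TOC is above -10" percent, in both populations.
- **Protocol 15.3 and Table 4:** the power calculation is made "using a non-inferiority margin of 10%, a one-sided alpha of 0.005, and the sample size methodology of Farrington and Manning".
- **SAP 4.1 and Table 3:** the same, "using an NI margin of 10%, a one-sided alpha of 0.005".

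The SAP states no EMA decision rule. Its introduction (1.1.1) leaves the EMA analysis to a separate SAP.

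**The concern.** A two-sided 99% interval corresponds to one-sided alpha 0.005, and a two-sided 95% interval to 0.025. Section 15.2.1 therefore calculates one interval and decides on another, and the level it decides on is not the one the trial was sized for. The only 95% intervals for microbiological success that the section specifies are unstratified and descriptive, with non-inferiority conclusions expressly ruled out. The rule thus refers to intervals that the EMA comparison does not produce.

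This is the confirmatory threshold for a regulatory claim. The two rules are nested: any result that passes at 99% also passes at 95%. They disagree over a band of results that could well occur. If the trial landed in that band, the sponsor could point to 15.2.1 and an assessor to the synopsis, and a choice made after unblinding would not be credible. The literal text is also the more lenient one, in favour of the test drug.

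**Working it through.** **Inputs**

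- Margin 10 points, one-sided alpha 0.005, Farrington-Manning method (Protocol 15.3, SAP 4.1).
- Success rates: "The microbiological success rates at TOC are assumed to be 79% and 82% in both treatment groups in the micro-MITT and ME populations, respectively".
- Evaluability: "it is assumed that 65% of the randomized subjects will be in the micro-MITT population and 60% in ME population". Of 1200 randomized 1:1, this gives 780 (390 per arm) and 720 (360 per arm).

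**Step 1. Alpha implied by each interval.** One-sided alpha = (1 - confidence level)/2.

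- 99%: (1 - 0.99)/2 = 0.005.
- 95%: (1 - 0.95)/2 = 0.025.
- Ratio: 0.025/0.005 = 5.

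**Step 2. Which level the stated power belongs to.** Farrington-Manning power = Φ[(δ + M - z·s0)/s1]. Here δ = 0 is the assumed true difference, M = 0.10 the margin, s0 the standard error under the restricted null and s1 the standard error under the alternative.

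For micro-MITT (79% vs 79%, 390 per arm), the restricted estimates at a difference of -0.10 are 0.7316 and 0.8316.

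- s0 = √[(0.7316×0.2684 + 0.8316×0.1684)/390] = 0.02937
- s1 = √[2×0.79×0.21/390] = 0.02917
- Alpha 0.005: (0.10 - 2.576×0.02937)/0.02917 = 0.835, so power is **79.8%**. The plan states 79.8%.
- Alpha 0.025: (0.10 - 1.960×0.02937)/0.02917 = 1.455, so power is **92.7%**.

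The plan's figure reproduces at 0.005 and not at 0.025. The sample size therefore assumes the 99% rule.

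For ME (82% vs 82%, 360 per arm) the same formula gives 81.1% at 0.005 and 93.4% at 0.025. The 84.7% in Table 4 does not reproduce from its own row; it is what 390 per arm would give. That is a separate point and does not change this one, since 81.1% still exceeds 80%.

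**Step 3. Probability of passing under each rule.** Exact binomial enumeration of the unstratified Miettinen-Nurminen test, margin 10 points, each population taken separately:

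| Population | True difference | 99% rule | 95% rule |
|---|---|---|---|
| micro-MITT (390 per arm, 79% control) | -10 points | 0.50% | 2.52% |
| | -5 points | 17.7% | 37.9% |
| | 0 | 80.1% | 92.9% |
| ME (360 per arm, 82% control) | -10 points | 0.49% | 2.51% |
| | 0 | 81.4% | 93.6% |

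**Step 4. Results on which the rules disagree.** Solve for the observed difference at which the Miettinen-Nurminen lower limit equals -10 points, with 390 per arm and 79% observed on control.

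- 99% interval: about -2.3 points.
- 95% interval: about -4.1 points.

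In whole subjects, take 308/390 successes on ertapenem. Eravacycline passes at 99% with 299 or more successes (-2.3 points) and at 95% with 293 or more (-3.8 points). Counts from 293 to 298 pass one rule and fail the other.

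**The case against.** The best defence is that the intended level is clear. The preceding sentence, the synopsis, both power sections and both power tables all point to 99%. The FDA paragraph just before has almost the same decision sentence, and 95% is correct there, so a copying slip is the likely cause. The separate EMA SAP is not among the documents and may already state 99%. SAP 1.2.2 breaks the blind only after database lock and a final SAP. The FDA primary analysis and the sample size are unaffected.

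Much of this stands. The slip is the probable explanation, and the surrounding text shows which value to restore. It does not cure the defect. A document still to be written supplies no rule now, and its author would naturally start from 15.2.1. The SAP does not say whether the finality condition on unblinding extends to the EMA SAP.

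Two limits on the numbers also stand. The 0.5% and 2.5% errors are per comparison. Because both populations must pass, they are upper bounds on the error of the joint claim, and the probabilities in the table are not those of the joint claim. In addition, the enumeration is unstratified, while 15.2.1 specifies the stratified form for the EMA. The nominal alpha is the same for both, but exact probabilities would shift somewhat.

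**Conclusion.** The concern holds: the EMA decision sentence in Protocol 15.2.1 is wrong as written. It sets the per-comparison one-sided alpha at 0.025 against a planned 0.005 and contradicts the sentence before it, the synopsis and the power calculation. In the micro-MITT population it roughly doubles the chance of passing when eravacycline is truly 5 points worse (37.9% against 17.7%). It also leaves a band about 1.8 points wide (-2.3 to -4.1) in which the conclusion depends on which sentence is followed. The factor of five is exact and needs no assumptions. The other figures assume 390 per arm, about 79% success on ertapenem and the unstratified method. This must be fixed before unblinding, because it is the threshold for a confirmatory claim.

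**What to change.** In Protocol 15.2.1, change 95% to 99% in the EMA decision sentence, so that non-inferiority is declared only if the lower limits of the two-sided 99% confidence intervals in both the micro-MITT and the ME population lie above -10%. Put the same rule in the EMA SAP and finalize that SAP before the blind is broken.

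The cost is a one-word protocol correction and alignment of one document. It needs no additional subjects or data. Planned power is not reduced: at 0.005 it is 79.8% (micro-MITT) and 81.1% (ME) at the stated numbers. Keeping 95% instead would mean rewriting the synopsis rule, the preceding sentence of 15.2.1, Protocol 15.3 and SAP 4.1.
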